Despite the considerable progress in the identification of effective biological therapies for the management of immune-mediated conditions, such as rheumatoid arthritis and inflammatory bowel disease, not much progress has been made in the identification of specifically targeted treatments for SLE (8, 101). In the EU and the USA, belimumab and anifrolumab are the only medicines approved for SLE in the last 60 years since hydroxychloroquine was approved for use in discoid lupus and SLE. Belimumab, was approved by the EMA in 2011, for the treatment of adult patients with active, autoantibody positive SLE with a high degree of disease activity (e.g., positive anti-dsDNA and low complement) despite standard therapy (33). It targets one pathway – the B-Lymphocyte stimulator (BLyS) cytokine pathway which affects B cell survival, maturation and differentiation into autoantibody producing cells (31). SLE patients are likely to have different underlying immunopathological pathways driving their SLE disease manifestations (32). As such, belimumab is not effective in all patients. Anifrolumab, a human monoclonal antibody that binds to subunit 1 of the type I interferon receptor (IFNAR1) was developed based on the evidence supporting the role of type I interferon pathway in SLE (48). It was approved in the USA and the EU as an add-on therapy for the treatment of adult patients with moderate to severe SLE, despite standard therapy in July 2021 and February 2022, respectively (38). Approval was based on clinical trial evidence from TULIP 1, TULIP 2 and Phase 2 MUSE which showed that monthly administration of anifrolumab led to a higher percentage of patients with a response, assessed with the British Isles Lupus Assessment Group (BILAG)–based Composite Lupus Assessment (BICLA), compared to patients who received placebo (48, 79).

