1. for MCM, end of first trimester
2. for all other outcomes, end of pregnancy

or occurrence of the outcome of interest (whichever comes first).

Exposure information will be derived from outpatient visits and/or prescription data, as recorded in the data source for each country. Country-specific cohorts of eligible women or

woman/offspring units will be identified, depending on the outcome of interest. A summary of the study design is presented in [Table 3](#).

Table 3: Summary of study design

Topic	Outcome	Population	Inclusion assessment window	Exposure assessment period	Index date	Follow-up	
						Offspring	Mother
Congenital anomalies	MCM	Live and non-live offspring	min 12 months prior to LMP2	from LMP2 to end of first trimester of pregnancy ¹	LMP2	from LMP2 to max 1y of age	NA
Select pregnancy loss outcomes	Composite of spontaneous abortion and stillbirth	All pregnancies	min 12 months prior to LMP2	from LMP2 to end of pregnancy ¹	LMP2	NA	end of pregnancy
Congenital anomalies	mCM	Live and non-live offspring	min 12 months prior to LMP2	from LMP2 to end of pregnancy ¹	LMP2	from LMP2 to max 1y of age	NA
Adverse pregnancy outcomes	Ectopic pregnancy	All pregnancies	min 12 months prior to LMP2	from LMP2 to end of pregnancy ¹	LMP2	NA	end of pregnancy
Adverse pregnancy outcomes	Spontaneous abortion	All pregnancies	min 12 months prior to LMP2	from LMP2 to end of pregnancy ¹	LMP2	NA	end of pregnancy
Adverse pregnancy outcomes	Elective termination of pregnancy	All pregnancies	min 12 months prior to LMP2	from LMP2 to end of pregnancy ¹	LMP2	NA	end of pregnancy
Adverse pregnancy outcomes	Stillbirth	All pregnancies	min 12 months prior to LMP2	from LMP2 to end of pregnancy ¹	LMP2	NA	end of pregnancy
Adverse pregnancy outcomes	Composite of foetal loss	All pregnancies	min 12 months prior to LMP2	from LMP2 to end of pregnancy ¹	LMP2	NA	end of pregnancy
Adverse pregnancy outcomes	Infections requiring hospitalisation during pregnancy	All pregnancies	min 12 months prior to LMP2	from LMP2 to end of pregnancy ¹	LMP2	NA	end of pregnancy
Adverse pregnancy outcomes	Emergency caesarean section	All pregnancies	min 12 months prior to LMP2	from LMP2 to end of pregnancy ¹	LMP2	NA	end of pregnancy
Adverse birth outcomes	Preterm birth	Live offspring	min 12 months prior to LMP2	from LMP2 to end of pregnancy	birth	NA	NA
Adverse birth outcomes	Small for gestational age	Live offspring	min 12 months prior to LMP2	from LMP2 to end of pregnancy	birth	NA	NA

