9.3.1 Exposure definition and measures

Study drugs

Exposure to anifrolumab and other SLE SOC drugs (see [Table 19](#)) will be ascertained from recordings of outpatient visits, procedures, prescriptions, prescriptions dispensed at community pharmacies, or insurance claims registrations, as available in the different data sources.

According to the drug indication, anifrolumab is expected to be prescribed as an IV infusion as part of polytherapy (i.e., add-on therapy to other SLE SOC drugs). However, due to the long study duration, the method of administration may change over time. Therefore, for the main analysis, the objectives will be evaluated in pregnancies exposed to anifrolumab in the polytherapy setting, regardless of administration route.

Despite that anifrolumab is indicated as an add on therapy, it is possible that some patients, either due to incomplete information on medication or off-label use, anifrolumab may be observed to have monotherapy. Therefore, a sensitivity analysis including anifrolumab exposure both as monotherapy and polytherapy will be performed. Details of this sensitivity analysis is provided in [Section 9.7.5](#).

Drug classes used in SLE SOC include antimalarials, glucocorticoids, immunosuppressants (both synthetic and biologic), immunoglobulins and plasmapheresis ([43](#), [55](#), [71](#)) ([Table 19](#)).

Co-medications ([43](#), [55](#)) (prescription drugs other than SLE SOC drugs in [Table 19](#)) are reported in [Table 27](#).

Classification of in utero exposure to SLE drugs and co-medications

The **window of clearance** is defined as 5 times the terminal half-life of the drug for SLE SOC and/or co-medication¹⁰, or, in certain cases, such as biologics, time for concentration to fall below the lowest level of quantification (LLOQ) for 95% of patients. LLOQ is 16 weeks for anifrolumab (2), 14 weeks for belimumab (60) and 15 weeks for rituximab (84).

Particular care will be taken in the definition and classification of *in utero* exposure of the offspring (i.e., through treatment received by the mother during or in the 16 weeks before pregnancy for anifrolumab, 14 weeks for belimumab, 15 weeks for rituximab, and 5-half-lives for other SLE SOC drugs).

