9.3.3 Participant's characteristics and potential confounders/risk factors

A broad range of characteristics and risk factors, related to mother and offspring, will be considered. These include, but are not limited to, demographic and clinical characteristics and concomitant comorbidities and medications (Objective 5). The final choice of characteristics, risk factors and confounders will depend on the availability of data and clinical relevance.

- **Demographic characteristics of the live offspring (at birth):** gender, gestational age, birth weight, Apgar score.
- **Demographic characteristics of mothers with SLE (before or at start of exposure):** maternal age, maternal socioeconomic status, and maternal ethnicity.
- **Maternal lifestyle characteristics (before or at LMP2):** smoking prior pregnancy, alcohol abuse prior pregnancy, substance abuse prior pregnancy, maternal weight and height or BMI (kg/m²) prior to pregnancy.
- **Maternal clinical characteristics:** SLE-related comorbid conditions, SLE SOC, SLE activity algorithm, co-medications (non-SLE SOC), selected autoimmune conditions (**before or at start of exposure**). Pre-pregnancy diabetes, pre-pregnancy hypertension (**before or at LMP2**).
- **Health Care Utilisation (HCU) (before or at LMP2)** in the 12 months prior to LMP2 will be use as proxy of burden of maternal comorbidities: number prenatal visits, number of outpatients and primary care visits, use of emergency department, hospitalisations (number of days, number of hospitalisations), type of health care providers visited.
- **Obstetric history (before or at LMP2):** gestational diabetes, pre-pregnancy pre-eclampsia, previous spontaneous abortion, previous stillbirth, previous preterm birth, and previous SGA birth.

The list of potential risk factors and confounders for the analysis of *MCM* and *mCM*, *adverse pregnancy outcomes* and *adverse birth outcomes* are summarised below in [Table 7](#), with further details in [Table 21](#). Factors listed as exclusion criteria for the selection of study population are

omitted from the potential risk factors ([Table 5](#)). The list of the ICD-10 codes for substance abuse, alcohol abuse, and diabetes, are presented in [Table 28](#), [Table 29](#), [Table 30](#), respectively.

Table 7: Potential confounders/risk factors of risk of MCM and mCM, adverse pregnancy outcomes and adverse birth outcomes in the offspring exposed *in utero* to anifrolumab vs unexposed *in utero* to anifrolumab

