	CM	Adverse pregnancy outcomes						Adverse birth outcomes	
	MCM/mCM	Ectopic pregnancy	Spontaneous abortion	Elective termination of pregnancy	Stillbirth	Infections requiring hospitalisation during pregnancy	Emergency C-section	Preterm birth	SGA
Mother									
Age at conception (LMP2)	×	×	×	×	×	×	×	×	×
Socioeconomic status (before or at start of exposure)	×	×	×	×	×	×	×	×	×
Health care utilisation (before or at LMP2)	×	×	×	×	×	×	×	×	×
SLE-related comorbid conditions (before or at start of exposure)	×	×	×	×	×	×	×	×	×
SLE SOC (before or at start of exposure)	×	×	×	×	×	×	×	×	×
SLE activity algorithm (before or at start of exposure)	×	×	×	×	×	×	×	×	×
Autoimmune conditions (before or at start of exposure)	×		×	×	×		×	×	×
Co-medications (non-SLE SOC) (before or at start of exposure)	×	×	×	×	×	×	×	×	×
Smoking (before or at LMP2)	×	×	×	×	×	×	×	×	×
Alcohol abuse (before or at LMP2)	×	×	×	×	×	×	×	×	×
Substance abuse (before or at LMP2)	×	×	×	×	×	×	×	×	×
Gestational diabetes (before or at LMP2)								×	×
Pre-pregnancy obesity (before or at LMP2)	×		×		×		×	×	×
History of pre-eclampsia (before or at LMP2)	×				×				
Pre-pregnancy hypertension (before or at LMP2)	×				×	×	×	×	×

	CM	Adverse pregnancy outcomes						Adverse birth outcomes	
	MCM/mCM	Ectopic pregnancy	Spontaneous abortion	Elective termination of pregnancy	Stillbirth	Infections requiring hospitalisation during pregnancy	Emergency C-section	Preterm birth	SGA
Mother									
Pre-pregnancy diabetes (before or at LMP2)	×		×		×	×	×	×	×
Previous spontaneous abortions (before or at LMP2)	×		×	×	×			×	
Previous stillbirth (before or at LMP2)	×				×				
Previous preterm birth (before or at LMP2)								×	
Previous SGA (before or at LMP2)									×
Offspring									
Year of conception	×	×	×	×	×	×	×	×	×

- Omitted from this list are potential risk factors and/or potential mediators between SLE treatments and CM that are exclusion criteria in this study (as defined in Section 9.2.2):
 - *mother*: history of CM or chromosomal abnormalities and genetic syndromes before delivery and women prescribed a confirmed teratogenic drug (including but not limited to warfarin, angiotensin converting enzyme inhibitors, antineoplastic agents, isotretinoin, misoprostol, or thalidomide), at LMP2 with a look back period of 5-half-lives of relevant drug, to account for prescriptions/dispensations/administrations that may have led to exposure during pregnancy.
 - *offspring*: adopted children.

SLE Severity and Activity Identification

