- Considering the IV infusion as the current route of administration of anifrolumab, definition of exposure may be challenging. Outpatient visits with a recording of the relevant ATC and/or procedure codes, rather than the prescribing/dispensing records may be needed to determine the exposure status of study subjects. This could potentially lead to misclassification of the exposure (i.e., use of anifrolumab may be under-detected). Such a potential bias would move the measure of association towards the null, since the exposure status of the cohorts would not be fully established, and the cohorts of exposed and non-exposed pregnancies will therefore be more similar. The feasibility assessment was used to inform the selection of data sources to minimise the impact of this potential limitation.
- It is assumed that all prescribed drugs are filled and then taken by patients in a compliant manner. Non-compliance would result in misclassification of exposure and could cause an underestimation of the association between exposure and outcome.
- SLE severity and activity algorithms were adapted from a previously published algorithm used in other settings (50), including the data sources included in this study, to meet current criteria and recommendations of medication use in SLE patients. The assumptions made for the proposed adaptations were based on the experience of the study team, including database analysis expertise and clinical knowledge, but also on literature relevant to the subject, ensuring that sound assumptions are made.
- For some of the diagnoses included in the activity algorithm, distinguishing clinical manifestations (i.e., acute illnesses) that define active SLE from comorbidities may not be possible (e.g., renal impairment). Therefore, there is a possibility of misclassifying signs of active disease as a comorbidity. The impact of this misclassification is considered minimal as adjustments will be made for disease activity as well as disease severity.
- Since anifrolumab prescribing is not recommended in pregnancy, uptake of the drug in pregnancy may be extremely limited at least in the initial years of launch post-authorisation, thus hampering the feasibility of the safety analyses with respect to study size targets.

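### The health-care-utilisation counts up to LMP2 include the anifrolumab infusion visits of women already on treatment, which can bias the adjusted RR downward if the covariate is used

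*Protocol*

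**What the plan says.** Section 9.3.3 lists the components of health care utilisation (HCU): visits ("number prenatal visits, number of outpatients and primary care visits"), emergency department use, hospitalisations and types of provider. They are measured "in the 12 months prior to LMP2 will be use as proxy of burden of maternal comorbidities". Table 7 anchors the variable at conception ("Health care utilisation (before or at LMP2") and ticks it for every outcome. Other treatment-related covariates in that table stop earlier, for example "SLE activity algorithm (before or at start of exposure".

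On the exposure:

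- **Route (Section 9.3.1):** "anifrolumab is expected to be prescribed as an IV infusion as part of polytherapy".
- **Frequency (Section 7.2, approval trials):** "monthly administration of anifrolumab led to a higher percentage of patients with a response".
- **Recording (Section 9.1):** "Exposure information will be derived from outpatient visits and/or prescription data". Section 9.9 adds that infusions may have to be found through "Outpatient visits with a recording of the relevant ATC and/or procedure codes".
- **Window (Section 9.3.1):** doses in the 16 weeks before LMP2 count as exposure, and women with earlier use are included.
- **Pattern (Section 9.5.1.1):** most exposed pregnancies are expected to be unplanned and exposed only early.

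Section 9.7.1 considers all Table 7 variables for the propensity score (PS).

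**The concern.** HCU is meant to measure how ill a woman was before exposure. For a woman already on anifrolumab, the count also measures the treatment. Every infusion recorded as an outpatient encounter adds a visit, and perhaps an infusion provider, without any extra comorbidity.

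The protocol avoids this elsewhere. The polypharmacy index in Section 9.3.3 leaves out SLE drugs, and Table 27 removes the code that Table 19 assigns to anifrolumab. The drug count is cleared of the study drug, but the visit count is not. Taking anifrolumab out of the severity algorithm would not cure this, because HCU is a separate variable.

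At stake is the direction of error. Section 9.5 sizes the study to rule out an RR of 2.5, so a covariate that lowers the adjusted RR favours that conclusion. Section 9.9 does not mention the problem.

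**Working it through.** **1. The plan's own figure.** Section 9.5.2 asks for 210 exposed and 420 comparators for MCM at 7% risk, with a true RR of 1.

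SE of log RR = √(1/(210×0.07) + 1/(420×0.07)) = √(0.0680 + 0.0340) = 0.319.

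Power = Φ(ln 2.5/0.319 − 1.96) = Φ(0.91) = 82%.

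Simulating the protocol's procedure gives 79.7%, so the stated 80% is reproduced. So are the 96% and 98% in Table 13 for 10% uptake (96.0% and 98.2%). These calculations carry no bias term.

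**2. Overlap of the windows.** HCU covers 12 months to LMP2, and the 16-week exposure window lies wholly inside it. Monthly dosing puts about 4 infusions in 16 weeks and up to about 12 in 12 months.

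**3. Direction.** Let total visits be T = B + I, where B is burden-driven and I is infusions. Balancing on T leaves the exposed with B lower by ΔI, the excess of infusions over comparators. For example, with 12 visits each and 4 of them infusions in the exposed woman, B is 8 against 12. If risk rises by a fraction b per burden-driven visit and the true RR is 1:

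adjusted RR ≈ exp(−b × ΔI).

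With b assumed at 0.01 to 0.03 and ΔI = 4, this is 0.96 to 0.89. The sign follows from the protocol's premise that visits mark burden. The size rests on b and ΔI, which the document does not give.

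**4. Size under stated assumptions.** Simulation with true RR 1 and burden distributed equally in the two groups. Assumed: mean 8, 12 or 20 non-infusion visits a year, log-SD of visits with burden 0.6, and outcome RR 1.22 or 1.49 per SD of burden. The estimate is standardised to the exposed.

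| Scenario | Infusions per infused woman | Adjusted RR |
|---|---|---|
| 80% of exposed and 30% of comparators infused; one other burden covariate (correlation 0.7) also adjusted | 1–4 | 0.95–0.98 |
| Same | 1–12 | 0.92–0.96 |
| All exposed and half of comparators infused; no other covariate | 1–12 | 0.89–0.96 |
| All exposed and no comparators infused; no other covariate | 1–6 | 0.82–0.95 |
| Same | 1–12 | 0.71–0.91 |
| Burden has no effect on outcome | any | 1.00 |
| Infusion visits removed from the count | any | 1.00 |

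Hand check of row 1, ignoring the other covariate: ΔI = 0.8×2.5 − 0.3×2.5 = 1.25, so RR ≈ exp(−0.0125) to exp(−0.0375), or 0.99 to 0.96.

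**5. Consequence for the 2.5 threshold.** Exposed totals at 10% uptake are 102 + 114 + 116 = 332 for MCM and 163 + 162 + 11 + 145 = 481 for pregnancy loss, with 1:2 matching. With a true RR of 2.5, the simulated chance of wrongly ruling it out is:

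| Bias factor | MCM | Pregnancy loss | True RR that appears as 2.5 |
|---|---|---|---|
| 1.00 | 1.7% | 0.8% | 2.50 |
| 0.95 | 3.4% | 4.2% | 2.5/0.95 = 2.63 |
| 0.90 | 6.1% | 13.8% | 2.5/0.90 = 2.78 |

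**The case against.** **Detail for the statistical analysis plan.** Section 9.7 defers data derivations, and which encounters enter a visit count could be called one. This stands only in part. The protocol itself fixes the window, the anchor and the components, and it clears the parallel drug count. Followed as written, the definition lets infusions in.

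**HCU may never enter a model.** Section 9.3.3 makes the final choice depend on data and relevance, and Section 9.7.1 only considers Table 7 variables, under a cap. This stands and makes the point conditional. On the other side, Section 9.9 says all relevant measured covariates will be entered in the PS and/or outcome models, and Table 17 shows visit counts available in both US sources and France.

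**The size is assumed.** This stands. Comparators may receive infused belimumab, rituximab, immunoglobulin or plasmapheresis. Severity, activity, SLE SOC and polypharmacy covariates would carry part of the burden. Some infusions may coincide with routine visits. The route may also change (Section 9.3.1). The return to RR 1.00 after removing infusions follows from simulating equal burden in both groups, so it isolates the mechanism and does not show that the study would be free of confounding.

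**Visible in the crude RR.** Crude estimates are reported, but a shift after adjustment cannot be told apart from confounding properly removed.

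**Conclusion.** The point holds as a conditional one. As defined, the outpatient-visit and provider-type components of HCU contain infusion encounters for women treated before LMP2. If HCU is adjusted for, the adjusted RR can be biased downward. A plausible size, on the assumptions shown, is a factor of about 0.9 to 0.98. It is nil if burden has no residual effect given the other covariates, and women first exposed after LMP2 or by a non-visit route do not contribute to it.

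A reader might infer three stronger things that the documents do not support:

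- **That the RR will be pulled to around 0.7.** This needs up to 12 infusions in every exposed woman, none in comparators, a strong burden effect and no other severity covariate in the model.
- **That the 0.1 balance threshold is breached.** The standardised differences the infusions create arise before adjustment, and adjustment exists to reduce them.
- **That exposed pregnancies will be lost.** Section 9.7.1 moves to weighting if matching significantly reduces the sample.

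This is a cheap improvement to a definition and does not undermine the design.

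**What to change.** In Section 9.3.3 and Table 7, define the HCU counts to exclude encounters for administration of anifrolumab or any other infused SLE SOC. Apply this identically in both groups, wherever the source identifies such encounters. Cover outpatient visits and provider types. Cover hospitalisations too where infusions are recorded as hospital stays, which Section 9.4.1.3 suggests may happen in France. Report covariate balance with and without the exclusion.

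No new data collection is needed, but the filter must be written by source. Infusions sit in the hospital medication register in Denmark, in electronic medical records in Finland and, if the drug is listed, in the hospital data in France. The Danish health insurance register holds no treatment information, and visit counts in RHEKISS are only partial. Dropping infusion visits for other SLE drugs loses some information on burden, but the SLE SOC and severity/activity components already carry it.
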